The potential benefit to the participant is that they would receive the treatment they normally would but with the potential benefit of less pain in the injection site with 1% lidocaine. As for the benefit to society, this may provide evidence that may change standard clinical practice with respect to how we perform benzathine penicillin G injections in the US and if lidocaine is shown to cause less pain, then it would become standard practice to include 1% lidocaine in each syringe of benzathine penicillin G.

2.f Early Withdrawal of Subjects, Including When and How to Withdraw Subjects

Early withdrawal of subjects will be handled by the principal investigator, with participants having the direct contact of the PI via email or phone, and through stating that they no longer would like to participate in the study. The PI also will have the right

to withdraw someone if upon evaluation of the patient, they meet certain exclusion criteria. All withdrawals will be done immediately and seeing as this study has short term

of participation, withdrawal should not be difficult.

2.g Data Collection and Follow-up for Withdrawn Subjects

Individuals who withdraw from the study will be noted as lost to follow up and no further data will be obtained from them. They will continue to receive standard of care within the outpatient clinical setting.

E3 Study Drug

3.a Description

1% lidocaine solution added to prefilled 1.2 million units Benzathine penicillin G.

3.b Treatment Regimen

0.5ml 1% lidocaine solution added to prefilled 1.2 million units Benzathine Pencillin G syringe

3.c Method for Assigning Subjects to Treatment Groups

Each participant will receive 2x 1.2 million units injection, one with lidocaine and one with normal saline, therefore each participant will serve as both treatment and control group.

3.d Preparation and Administration of Study Drug

Each syringe of BPG is prefilled. A nurse/MA will then add 0.5 ml 1% lidocaine solution to one BPG syringe, and 0.5ml normal saline solution to another BPG syringe. They will randomly syringes to be injected into the left gluteal muscle vs the right gluteal muscle via random assignment program. They will log the assignment with the unique patient code into a log book.

3.e Subject Compliance Monitoring

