Each log book entry will be entered into RedCap survey using the unique patient code and then the patient will fill out pain scale in RedCap using their unique code 10 minutes and 24 hours after injection through follow up email. If they do not respond to the 24 hour follow up email, a second email will be sent 48 hours after injection.

3.f Prior and Concomitant Therapy

Participants will be asked in the follow up survey about any other pain medications they have taken within the last 24 hours. They will also be asked about if this is their first treatment with respect to syphilis treatment, or if this is the second or third dose in a series of treatment. No other concomitant therapies would preclude individuals from participating in the study.

3.g Packaging

Both BPG syringes will look identical other than having one say L and one say R, based off randomization.

3.h Blinding of Study Drug

Both participants and clinicians will be blinded to the contents of the syringe. The nurse filling the syringe will assign the syringes randomly to be injected into L or R gluteal muscle and will label them accordingly, logging the designation in a log book that will remain blinded until the analysis portion of the study. The participant will be blinded as they will receive one site of injection with lidocaine and the other with normal saline, serving as their own intervention and control group.

3.i Receiving, Storage, Disposing and Return

BPG will be stored in the refrigerator in the Washington University St. Louis Infectious Diseases clinic, along with the lidocaine and normal saline solutions being kept in storage in the same clinic. All syringes will be disposed of in sharps containers, as well as used lidocaine ampules and normal saline syringes.

F Study Procedures

F1 Screening for Eligibility and Visit 1 (completed at one visit)

- 1- Participants with confirmed syphilis (RPR and treponemal test positive) who are receiving their first treatment injection of bicillin will be screened for participation in the study by infectious diseases clinicians, nurses, or Mas who interact with the patient during their injection visit. If patient is willing to participate, trial team will be notified. (15-30 minutes)
- 2- Trial team will assess patient for inclusion/exclusion criteria and ask if would like to be part of clinical trial. (5 minutes)

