Adverse events can be reported within 7 days post injection with participants having the ability to call for up to 7 days.

3.h Post-study Adverse Event

Any adverse event post study or the time listed above should be reported to the PI.

F4 Study Outcome Measurements and Ascertainment

The primary outcome measure will be pain rating scores from 0 (least pain) to 10 (most pain) at 10 minutes after injection in each injection site, as well as 24 hours after injection.

Secondary outcome measures will include adverse effects of lidocaine or benzathine penicillin G., such as allergic reactions or injection site reactions.

F5 Rationale for the Selection of Outcome Measures

Injection site pain is the most common adverse effect of Benzathine Penicillin G (BPG) intramuscular injections. For this reason, rating pain scales from 0-1 10 minutes and 24 hours after injection will allow us to measure immediate and longer term pain after injection, with and without lidocaine added to prefilled BPG syringes.

G Statistical Plan

G1 Sample Size Determination and Power

A sample size of 46 patients (92 injections) will be required to detect a clinically significant reduction in pain and discomfort associated with the injection of Bicillin, with a power of 80% and a significance level of 0.05.

G2 Interim Monitoring and Early Stopping

As this is a short term study with small population, it is not expected to stop early. Interim monitoring for adverse effects will occur at 6 months or after 24 participants have participated, whichever occurs first.

G3 Analysis Plan

Pain scores will be collected by trained study personnel. Data will be entered into a secure database and analyzed using statistical software. Descriptive statistics will be used to summarize the data, and t-tests or chi-squared tests will be used to compare pain scores and adverse effects between the treatment and control groups. They will also see if there any use of pain medications through descriptive statistics. Demographic data will also be collected.

G4 Statistical Methods

Descriptive statistics will be used to summarize the data, and t-tests or chi-squared tests will be used to compare pain scores and adverse effects between the treatment and control groups.

G5 Missing Outcome Data

Missing outcome data on follow up will be noted and statistical analysis will be performed on intention to treat model.

G6 Unblinding Procedures

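### G5 answers missing 24-hour scores with intention to treat, which does not handle unanswered surveys, so the 24-hour primary comparison defaults to those who replied

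*Protocol*

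**What the plan says.** F4 makes the primary outcome the 0–10 pain score at each site at 10 minutes, "as well as 24 hours after injection". The design is within-person: "each participant will serve as both treatment and control group" (E3, 3.c).

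The 24-hour score comes from an emailed REDCap survey. On non-response, E3 3.e says: "If they do not respond to the 24 hour follow up email, a second email will be sent 48 hours after injection". For withdrawals, E2 2.g says: "Individuals who withdraw from the study will be noted as lost to follow up and no further data will be obtained from them".

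The analysis is described in G3 and G4: "t-tests or chi-squared tests will be used to compare pain scores and adverse effects between the treatment and control groups". Neither section says whether the t-test is paired. G5, headed Missing Outcome Data, reads in full: "Missing outcome data on follow up will be noted and statistical analysis will be performed on intention to treat model". The protocol contains no imputation rule, likelihood-based model, missingness assumption or sensitivity analysis. G1 states the size without a non-response allowance: "A sample size of 46 patients (92 injections) will be required to detect a clinically significant reduction in pain and discomfort", at 80% power and a significance level of 0.05.

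**The concern.** Intention to treat answers the question of which assignment a site is analysed under. It does not say what to do when there is no score. G5 sets out to deal with missing outcomes and names a principle that cannot do so. Combined with a t-test, which uses only observed scores, the plan leads by default to a responders-only 24-hour comparison carrying an intention-to-treat label.

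The exposure is all at 24 hours. One unanswered survey loses both sites of that participant. F1, step 4, has the 10-minute scores taken during the clinic visit, so nearly everyone should have them, and they show how non-responders differed from responders. G5 makes no use of them. If people in more (or less) pain reply more often, and lidocaine's benefit varies with the amount of pain, the reported 24-hour difference describes those who replied.

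**Working it through.** **1. The plan's own figure.** G1 gives no effect size, SD, sidedness or dropout rate, so 46 cannot be reproduced, only back-solved. Assuming a two-sided paired t-test with n = 46, alpha 0.05 and 80% power, the implied standardised within-pair difference is 0.42. The normal approximation (1.96 + 0.84)/√46 gives 0.41.

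**2. Power on the pairs left.** The non-response rates d are assumptions; the protocol gives none. Pairs left = 46(1 − d). Power is that of the paired t-test at the implied difference of 0.42. Enrolment needed to keep 46 pairs = 46/(1 − d), rounded up.

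| d | Pairs left | Power | Enrol to keep 46 |
|---|---|---|---|
| 0% | 46 | 80% | 46 |
| 10% | 41 | 75% | 52 |
| 20% | 37 | 71% | 58 |
| 30% | 32 | 64% | 66 |
| 40% | 28 | 58% | 77 |

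This holds only if 46 was meant as the evaluable number.

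**3. Bias when reply depends on average 10-minute pain.** One large simulation assumed 400,000 participants, scores truncated to 0–10, lidocaine removing 30% of pain and a true 24-hour difference of about −0.85. Relative bias = complete-case difference/(−0.85) − 1.

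| Odds of reply per point of pain | 75% reply | 60% reply |
|---|---|---|
| ×1.25 | −0.886 (4% too large) | −0.901 (6%) |
| ×1.5 | −0.905 (6%) | −0.935 (10%) |
| ×2 | −0.930 (9%) | −0.971 (14%) |
| ×0.67 | −0.797 (6% too small) | −0.772 (9% too small) |

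Repeats with other assumed means and SDs gave about 3% to 21% for a proportional effect. For a constant effect they gave about 1% to 7%, mostly because scores cannot go below zero. With a constant effect and no truncation, reply driven by average pain gave no bias (0.90 against a true 0.90).

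**4. Size against sampling error.** The largest tabulated error is 0.971 − 0.85 = 0.12 points. With a standard error of about 0.25 at 34 pairs (from assumed SDs), that is 0.12/0.25 ≈ 0.5 standard errors. Even 21% of 0.85, or 0.18 points, is about 0.7.

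**5. What the 10-minute scores recover.** When reply was generated from the 10-minute scores, conditioning on them cut the bias to about 2% or less. That is partly built in, since the model conditions on exactly what drove reply. When reply was driven by 24-hour pain instead (proportional effect), 3% to 14% remained, against 5% to 20% for complete cases.

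**6. Precision.** Let r be the correlation between the 10-minute and 24-hour within-pair differences. With 34 of 46 replying, the variance ratio to the complete-case estimate is (1 − r²) + r² × 34/46:

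- r = 0.7: 0.51 + 0.49 × 0.739 = 0.872
- r = 0.5: 0.75 + 0.25 × 0.739 = 0.935
- r = 0.09: 0.992 + 0.008 × 0.739 = 0.998

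The formula ignores the cost of estimating the covariance. Simulation at n = 46 gave anything from 2% worse to 7% better. The documents give no value of r.

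**The case against.** The missing-data method and estimation model are ordinary content of a statistical analysis plan, and that plan is not shown. Read separately, the two halves of G5 are not false: missingness is noted, and sites are analysed as assigned. This stands as far as it goes. No fault lies in the absence of an imputation rule as such. What remains is that G5 does address missing data and names a concept that cannot handle it, so it would need correcting even if another document supplied a method.

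A reader might infer several stronger things that the documents do not support:

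- **That the protocol says non-responders are dropped.** It does not. This follows from a t-test with no other method named, and a t-test can be preceded by imputation.
- **That non-response goes unaddressed.** E3 3.e sends a reminder at 48 hours, which should recover some replies. Reply rates of 60% to 75% are assumptions.
- **That missing data could unbalance the arms.** One survey covers both sites, so pairs are lost whole.
- **That the bias is large.** Larger figures do arise if reply depends on the saline site alone (1.03 to 1.25 against a true 0.90) or on the within-pair difference (1.17 to 1.61). But participants are blinded to side. If reply depended on the worse site, which a blinded participant can know, the result was 0.94 to 1.01, about 5% to 12% too large.
- **That a mixed model removes the bias or reliably gains precision.** Steps 5 and 6 of the working show otherwise.

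One further caution stands. F1 has the 10-minute scores taken in clinic, while E3 3.e mentions the 10-minute and 24-hour scores together with the follow-up email. The benefit of the fix depends on the in-clinic reading.

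**Conclusion.** The point holds in a limited form. G5 names analysis by assignment where a way of handling unanswered 24-hour surveys is needed, and the default for one of the two primary time points is a responders-only test. Calling that intention to treat would misdescribe it even if no bias arose.

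The expected distortion is modest: about 1% to 7% of the difference with a constant effect and 3% to 21% with a proportional one, below one standard error in the cases worked. These ranges rest on assumed reply rates, assumed dependence of reply on average 10-minute pain, and assumed means and SDs. The loss of power in step 2 is the cost of the missing pairs themselves; a better analysis recovers little of it unless the 10-minute and 24-hour differences correlate well. This should be corrected, but it does not threaten the trial's validity.

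**What to change.** Reword G5 to state that:

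- sites are analysed by randomised side;
- the 24-hour lidocaine-minus-saline contrast comes from a linear mixed model of all four scores per participant, including everyone with at least one score, with treatment, time and treatment-by-time effects, unstructured within-person covariance and small-sample degrees of freedom such as Kenward-Roger;
- the complete-pair paired t-test is a sensitivity analysis;
- the number contributing at 24 hours is reported, and the responders-only test is not called intention to treat.

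The same edit should say whether a reply to the 48-hour reminder counts as the 24-hour score, and confirm that the 10-minute scores are collected in clinic. All of this should be settled before unblinding, so that the handling of non-responders is not chosen with results in view.

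The cost is a paragraph of wording and one standard model, with no new data. The model assumes that missingness is explained by the 10-minute scores. It reduces but does not remove bias if reply depends on 24-hour pain itself, and it may cost 1% to 2% in variance if the correlation is near zero.
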